15.3 Deaths, Other Serious Adverse Events, and Other Significant Adverse Events

Listings will be presented for the following types of AEs:

- TEAEs leading to death, including flags for death within 30 days of last dose of IMP
- TEAES with CTCAE grade ≥ 3
- Serious TEAEs
- TEAEs leading to withdrawal, dose interruption or dose reduction of trial drug

15.3.1 Deaths

Deaths will be listed using the Safety Analysis Set, displaying by dose group the following:

- Deaths by primary reason of death
- Flags for death within 30 days of last dose of IMP.

15.4 Clinical Laboratory Evaluation

The safety population will be used for all clinical laboratory evaluations.

All laboratory results (biochemistry, hematology, coagulation, urinalysis, pregnancy test), will be listed by subject and time point. The following information will be included in the listing:

- Sex of subject
- Date/time of sample
- Treatment day
- Result
- Reference range (for continuous variables)
- Flag for values above ("H") or below ("L") the reference range (for continuous variables)
- Change from baseline (for continuous variables)
- NCI-CTCAE grade
- Flag for value with worst-on trial grade ("Y")

All continuous laboratory results will be summarized by dose and time point, including absolute values and change from baseline.

Laboratory results will also be classified by Grade according to NCI-CTCAE. The worst post-baseline on-trial Grades will be summarized, as well as the worst post-baseline Grades within the first cycle. Shifts in toxicity grading from first treatment to highest Grade will be displayed: number of subjects with shift to any higher grade, to higher grade 3 or 4, to higher grade 4.

Results for variables that are not part of NCI-CTCAE will be presented as below, within, or above normal limits. Only subjects with post-baseline laboratory values will be included in these analyses.

D-dimer results will be listed with biochemistry.

15.5 Vital Signs

The safety population will be used for all vital sign evaluation. Vital signs will be listed, including the following information:

- Date/Time of assessment
- Systolic blood pressure (mmHg)
- Diastolic blood pressure (mmHg)
- Position in which blood pressure was taken
- Heart rate (bpm)
- Temperature
- Respiratory rate (breaths/minute)
- Change from baseline for continuous variables
- Weight

All continuous variables will be summarized descriptively by dose group and time point, including absolute values and change from baseline.

15.6 Lower Extremity Doppler Ultrasonography

The results of the lower extremity Doppler Ultrasonography will be listed by dose group and time point using the safety population and include the following information:

- Date/Time of assessment
- Whether deep vein thrombosis (DVT) was detected
- Location of DVT
- Size of DVT (cm)

15.7 ECG

All analysis of electrocardiogram (ECG) data will be based on the safety population.

Triplicate values will be handled as follows: listings will contain the individual triplicates and the aggregated results. Summaries will only use the aggregated values. The aggregation of triplicate ECGs will be performed using the arithmetic mean for all parameters at each time point. The aggregated values of the last triplicate ECG measurement prior to first trial drug administration will be used as the baseline measurement.

Results will be listed, including the following information:

- Time point
- Time of measurement
- Position
- Heart rate (beats/min)
- PQ/PR duration (ms)
- RR duration (ms)
- QRS duration (ms)
- QT corrected using Fridericia's formula: QTcF = QT/ $\sqrt[3]{RR}$ (ms)
- Rhythm evaluation
- Whether ECG is abnormal
- Clinical significance if ECG is abnormal

Potentially clinically significant abnormal values of ECG will be flagged according to the following criteria:

Parameter	Potentially Clinically Significant Abnormalities (PCSA) Criteria
Heart rate	≤ 50 bpm and decrease from baseline ≥ 20 bpm ≥ 120 bpm and increase from baseline ≥ 20 bpm
PQ/PR	≥ 220 ms and increase from baseline ≥ 20 ms
QRS	≥ 120 ms
QTcF absolute	Prolonged: >450 ms (Male), >470 ms (Female) Potentially significant abnormality: ≥ 500 ms
QTcF change from baseline	Prolonged: Increase from baseline > 60 ms

Only the aggregated measurement will be flagged as described. The flagging of the aggregated measurement will be performed by applying the above rules directly on the averaged ECG parameters.

For display of overall assessment of the result of the ECG as normal, abnormal not clinically significant, and abnormal clinically significant, the worst result of the triplicates will be considered for the analysis of the aggregated measurements.

The ECG parameters will be summarized by descriptive statistics per time point including absolute values and change from baseline. Number and percentages for subjects meeting the PCSA Criteria will also be provided. For the investigator's overall ECG assessment, a shift table from baseline to the worst on-treatment result will be created.

Data will be further analyzed using concentration effect modeling for baseline corrected QTcF values. Change from baseline (QTcF) will be modelled using a linear mixed model, with baseline QTcF value and drug concentration as continuous covariates, and subject as a random factor, using data from the first cycle, and additionally using all data until cut-off. One model will be run using an unstructured covariance matrix, another one using the compound-symmetry structure. The estimate for the concentration coefficient will be reported, including standard error, degrees of freedom and 95% confidence interval for the coefficient. The concentration effect model will be fit using the PK analysis set. The SAS code for this analysis can be found in the TFL shells.

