5.3.2 Exclusion Criteria

5.3.2.1 Part 1, M8891 Single Agent, Solid Tumors

For Part 1, subjects are excluded from the study if any of the following criteria apply:

1. Eastern Cooperative Oncology Group Performance Status (ECOG PS) ≥ 2
2. Bone marrow impairment as evidenced by hemoglobin < 9.0 g/dL, neutrophil count $< 1.5 \times 10^9/L$, platelets $< 100 \times 10^9/L$. Transfusion is not allowed within 3 weeks before first dose
3. Renal impairment as evidenced by calculated creatinine clearance < 60 mL/min (according to the Cockcroft-Gault formula)
4. Liver function abnormality as defined by total bilirubin $> 1.5 \times$ ULN, or AST/ALT $> 2.5 \times$ ULN, for subjects with liver involvement AST/ALT $> 5 \times$ ULN
5. Extensive prior radiotherapy to more than 30% of bone marrow reserves, or prior bone marrow/stem cell transplantation within 5 years of study start
6. Clinically significant cardiac conduction abnormalities, including QTcF interval prolongation of > 480 ms and/or pacemaker or impaired cardiovascular function such as New York Heart Association classification score > 2
7. Thromboembolic events requiring therapeutic anticoagulation. Concomitant anticoagulation at therapeutic doses with oral anticoagulants (i.e., warfarin, direct thrombin

and Factor Xa inhibitors) or platelet inhibitors (i.e., clopidogrel) started within the last 6 months of screening.

Note: Low dose aspirin for cardio-protection and low dose LMWH are permitted (in subjects who are on a stable dose of LMWH for at least 6 weeks before the first dose of study treatment, and who have had no clinically significant hemorrhagic complications from the anticoagulation regimen or the tumor).

[figure not shown]
8. Pregnant or nursing female subject
9. Any other severe clinical condition that in the opinion of the treating physician may compromise the trial participation
10. Subjects used any investigational agents 14-28 days or 5-half-lives (whichever is shorter) of the initiating study treatment
11. History of difficulty swallowing, malabsorption, or other chronic gastrointestinal disease or conditions that may hamper compliance and/or absorption of the investigational drugs
12. Life expectancy < 3 months
13. Known hypersensitivity to the trial treatment or to one or more of the excipients used
14. Legal incapacity or limited legal capacity.

5.3.2.2

Part 2, M8891 combined with Cabozantinib, mRCC

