7.4.5.1 Part 1 M8891 Single Agent, Solid Tumors

ECGs for QT/QTc Evaluation

At screening, standard triplicate (within 2 min) digital 12-lead ECG will be obtained after the subject has been rested in semi-recumbent position for at least 5 min using standard 12-lead equipment to determine the QTcF interval. If the average of these three consecutive results for QTcF interval is > 480 ms the subject does not meet eligibility in this regard.

12-lead triplicate digital ECG will be performed within 2-minutes after at least 10 minutes rest in supine position, on Cycle 1 Day 1 and Day 15 at pre-dose and 1, 2, 4, 5, 6, 8, 12 hours and 24 hours post-dose (\pm 15 minutes) and on pre-dose on Day 8. The SMC may decide that the Day 15/Day 16 assessment can be waived in case no relevant drug accumulation is being observed. ECG assessments at subsequent cycles will be performed pre-dose at time points as indicated in Table 1. ECGs should be performed directly before PK sampling time-points on days where both assessments are performed.

Digital ECGs will be stored for a later independent analysis: ECG extractions will be made by the central ECG laboratory and over-read of interval measurements will be provided by experienced, qualified, and certified cardiac safety specialists. The readers will be blinded to subject details, treatment, visit day, and time points of the ECG recording, and a single reader will read all ECGs of a given subject. Time-matched, replicate ECGs and PK samples collected will be used to analyze for QTcF interval responses using slope analysis of exposure/response. This analysis may be reported separately.

7.4.5.2

Part 2 M8891 with cabozantinib, mRCC

Safety ECGs

Safety ECGs are standard triplicate 12-lead ECGs obtained for safety monitoring according to the SoAs (Table 4 for Part 2A and Table 5 for Part 2B). Subjects will rest in semi-recumbent position for at least 5 minutes. Safety ECGs will be read locally, and all ECGs should be assessed on the day of collection to determine continued eligibility. The calculated QTcF interval average of 3 12-lead ECGs must be \leq 450 ms for males and \leq 470 ms for female participants' eligibility. To confirm suitability for treatment after screening, ECGs must be repeated on Day -1, Cycle 1, prior to administering the first dose of study treatment unless the screening tests were performed within 14 days prior to first dose.

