206	Important	Inc/Excl Criteria	Observable	Clinically significant cardiac conduction abnormalities, including QTc prolongation of > 480 msec and/or pacemaker or impaired cardiovascular function such as New York Heart Association classification score > 2, however subject is included in the trial.	Source Data Review	Yes
		Inc/Excl		Any other severe clinical condition that in the opinion of the treating physician may compromise the trial participation, however subject is included in the	Source Data	
207	Important	Inc/Excl Criteria	Observable Observable	trial. Participation in another clinical trial within the past 28 days, however subject is included in the trial.	Source Data Review	Yes

PD REF ID	Category (DVCAT)	Classification (DVDECOD)	Type of Deviation Observable/ Programmable (Data Driven)	PD (DVTERM	PD Identification Method Options	cIPD ?
				History of difficulty swallowing, malabsorption, or other chronic gastrointestinal disease or conditions that may hamper compliance and/or absorption of the		
209	Important	Inc/Excl Criteria	Observable	investigational drugs, however subject is included in the trial.	Source Data Review	
210	Important	Inc/Excl Criteria	Observable	Life expectancy < 3 months, however subject is included in the trial.	Source Data Review	
211	Important	Inc/Excl Criteria	Observable	Known hypersensitivity to the trial treatment or to one or more of the excipients used, however subject is included in the trial.	Source Data Review	
212	Important	Inc/Excl Criteria	Observable	Legal incapacity or limited legal capacity, however subject is included in the trial.	Source Data Review	
213	Important	Inc/Excl Criteria	Observable	The subject is a female of childbearing potential who is pregnant, breastfeeding or who did not agree to use effective contraceptive measures from time of informed consent through 92 days after last dose of study drug.	Source Data Review	
214	Important	Inc/Excl Criteria	Observable	The subject is male with partners of childbearing potential that did not use barrier contraception and did not have their partners use another method of contraception from the time of informed consent through 92 days after last dose of study drug.	Source Data Review	
215		Inc/Excl Criteria	Programmable	Eastern Cooperative Oncology Group Performance Status (ECOG PS) is not <2 however subject is included in study	On-Line Check	

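### The lower absolute QTcF tier and the QRS criterion in SAP 15.7 have no baseline condition, so Part 1 subjects already above the cut-off before dosing are counted as meeting it

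*SAP*

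**What the plan says.** **Entry limit.** Protocol 5.3.2.1, criterion 6, excludes clinically significant conduction abnormalities, "including QTcF interval prolongation of > 480 ms and/or pacemaker". Protocol 7.4.5.1 applies the same limit to the mean of the screening triplicate: if the "QTcF interval is > 480 ms the subject does not meet eligibility". The SAP's own deviation list (18.1, item 206) repeats the figure: "including QTc prolongation of > 480 msec and/or pacemaker". Neither document sets a numeric QRS limit for Part 1 entry.

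**Reporting criteria.** SAP 15.7 lists criteria for potentially clinically significant ECG values, applied to the triplicate means:

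- QTcF absolute, lower tier: "Prolonged: >450 ms (Male), >470 ms (Female"
- QTcF absolute, upper tier: "Potentially significant abnormality: ≥ 500 ms"
- QTcF change, as a separate row: "Prolonged: Increase from baseline > 60 ms"
- PQ/PR: "≥ 220 ms and increase from baseline ≥ 20 ms"
- Heart rate: an extreme value together with a change of at least 20 bpm
- QRS: 120 ms or more, with no change condition

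**Output.** "Number and percentages for subjects meeting the PCSA Criteria will also be provided". The section does not restrict the count to values that are new after dosing. Its only ECG shift table is for the investigator's overall rating.

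**The concern.** The entry limit lies above the lower reporting cut-off by 30 ms for men (480 − 450) and 10 ms for women (480 − 470). A subject can be eligible and already prolonged in the SAP's sense. That subject then appears in the dose-group percentage as one more prolonged case, and nothing in the table separates the case from a rise after dosing. The same applies to a subject who enters with QRS of 120 ms or more that was not judged clinically significant.

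The rest of the SAP usually makes this separation. Treatment-emergent adverse events must begin or worsen after dosing (15.2), laboratory grades are shown as shifts (15.4), ECOG status is shown as shifts (14.3), and two other rows of this ECG table require a change from baseline.

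ECG change is a Part 1 secondary endpoint, and protocol 3.3.1 says that QTcF prolongation is being investigated in Part 1. With cohorts of 3, one pre-existing case can dominate the percentage for a dose level. A reader could take it for a drug effect, or could discount a real new case as pre-existing.

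**Working it through.** The documents give no expected QTcF abnormality rate, so there is no planned figure to reproduce. The check compares the limits and then illustrates the size.

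**1. Weight of one subject.** Cohort size is 3 (protocol 5.1.3.1). Dose levels of 6 or 9 appear in the scenario in protocol 8.1.1, with a total of about 36 and a maximum of 42. One subject counted only because of the baseline value adds 100/n points:

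| n | 3 | 6 | 9 | 36 | 42 |
|---|---|---|---|---|---|
| Points | 33.3 | 16.7 | 11.1 | 2.8 | 2.4 |

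**2. Effect on a pooled rate.** Let q be the share who enter above the cut-off (all counted) and e the new-onset rate in the rest. The crude rate is q + (1 − q)e. The documents give neither q nor e; the values below are assumptions.

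- q = 0: the crude rate equals e, so there is no inflation.
- q = 5%, e = 5%: 0.05 + 0.95 × 0.05 = 9.8% crude, against 5% new onset.
- q = 10%, e = 5%: 0.10 + 0.90 × 0.05 = 14.5% crude, against 5%.
- q = 10%, e = 0: 10% crude, against 0%.

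In subjects, q = 5% is 1.8 of 36 or 2.1 of 42; q = 10% is 3.6 or 4.2.

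**3. Would a subject who enters above the cut-off be counted on treatment?** Protocol 7.4.5.1 gives 8 post-dose triplicates on Day 1, one on Day 8, and a pre-dose plus 8 post-dose on Day 15: 8 + 1 + 9 = 18 after the first dose in Cycle 1. Assume no drug effect, a normal distribution, a within-subject SD s for the triplicate mean, and independent time points. For a man with usual value m:

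P(at least one above 450) = 1 − Φ((450 − m)/s)^18

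- m = 455 to 480 ms, s = 5 to 12 ms: about 1.00.
- m = 440 ms, s = 6 to 10 ms: 0.59 to 0.96.
- m = 430 ms, s = 6 to 10 ms: 0.01 to 0.34.

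For women, add 20 ms to m. The last two lines describe ordinary variation in subjects below the cut-off, which is a different matter from the entry overlap.

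**4. The other QTcF criteria under the same model.**

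- Increase above 60 ms: the difference has SD s√2. At s = 12 ms the chance per comparison is 1 − Φ(60/17.0) = 0.0002, and less for smaller s.
- 500 ms or more: at m = 470 ms and s = 8 ms the 18-look probability is 0.0016. It matters only near the entry limit or with large variability: at m = 480 ms it is 0.0006, 0.11 and 0.59 for s = 5, 8 and 12 ms.

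**The case against.** The strongest case is that little hangs on this count.

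- The SAP labels the lower tier only as prolonged and keeps the stronger label for the upper tier, which lies above the entry limit. A separate row captures change from baseline.
- SAP 15.7 also summarises absolute values and changes per time point, lists every triplicate, and models change in QTcF with baseline QTcF as a covariate. In a 3-subject group a reader can look up each pre-dose value.
- All analyses are descriptive (SAP 9), the primary endpoint is DLTs, and SMC outputs are defined in a separate plan (SAP 4).
- The PCSA sentence does not say whether subjects are counted per time point or ever on treatment, and the table shells are not available. If counts are per time point and include baseline, pre-dose exceedances would be visible and the 18-look calculation would not apply.
- The SMC may waive the Day 15/16 ECGs. With 9 looks, the 440 ms figure falls to 0.36–0.79 and the 430 ms figure to 0.004–0.19. Correlation between same-day ECGs would lower them further.

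Most of this stands, and it limits the consequence. A reader might infer that the main QTcF assessment of Part 1 is biased, or that a false signal follows directly. The documents do not support that: this tier is one of three QTcF criteria, and the exposure–response analysis is adjusted for baseline. Nor do they show that any subject entered in the overlap.

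What does not fall away is that no planned summary links a subject's baseline QTcF category to the worst category after dosing. Even counts per time point with a baseline column would not make that link. As a count of subjects with a value above the cut-off, the percentage is literally correct; it misleads only when read as an on-treatment effect, which is how a safety table by dose group is likely to be read.

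**Conclusion.** The mismatch is established by the text: entry is allowed up to 480 ms, while the lower absolute tier starts above 450 ms for men and 470 ms for women with no baseline condition, and QRS likewise has none. Each subject who enters above the cut-off is worth 33 points in a dose group of 3. The total effect is proportional to the number of such subjects, which the documents do not give, and it is zero if there are none.

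The near-certain count for a man at 455 ms or above holds over SDs of 5–12 ms and, at 455 ms, does not depend on having all 18 looks. The figures at 430–440 ms depend on assumed SDs, independence and the number of looks. They should not be used as evidence of inflation from the entry limit.

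This concerns the reading of one descriptive safety table. No error rate, sample size, dose decision or eligibility rule is affected.

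**What to change.** In SAP 15.7, add for each dose group a table of baseline category by worst post-baseline category, using the SAP's own cut-offs:

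- **QTcF:** at or below 450/470 ms; above 450/470 to below 500 ms; 500 ms or more.
- **QRS:** below 120 ms; 120 ms or more.

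Report new-onset counts, with subjects whose baseline did not meet the criterion as the denominator, beside the existing crude counts. State whether counts are per time point or ever on treatment. Keep the crude counts and the 60 ms change row: a move from 455 to 479 ms in a man stays within one category and would vanish from a new-onset count alone.

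The cost is some SAP wording and a larger table; all the data are already collected. Two limits remain. Subjects just below the cut-off will still cross it by ordinary variation. And a man whose usual value is 455 ms has a single baseline triplicate at or below 450 ms with probability Φ(−5/s), which is 0.20 to 0.31 for s = 6 to 10 ms, and could then be labelled new onset. The entry limit itself is not questioned here.

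### The SAP's concentration-QTcF model names no by-subject slope and no primary fit, and its unstructured/compound-symmetry pair leaves at best one usable model, a random-intercept fit whose interval may be too narrow

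*SAP*

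**What the plan says.** SAP 15.7 fits a linear mixed model to change from baseline in QTcF, "with baseline QTcF value and drug concentration as continuous covariates, and subject as a random factor", run "using data from the first cycle, and additionally using all data until cut-off". On the covariance it says: "One model will be run using an unstructured covariance matrix, another one using the compound-symmetry structure". The output is set as follows: "The estimate for the concentration coefficient will be reported, including standard error, degrees of freedom and 95% confidence interval for the coefficient". For everything else it points elsewhere: "The SAS code for this analysis can be found in the TFL shells".

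Two further passages fix how many repeated values each subject contributes. SAP 15.7 defines baseline: "The aggregated values of the last triplicate ECG measurement prior to first trial drug administration will be used as the baseline measurement". Protocol 7.4.5.1 schedules Part 1 ECGs "on Cycle 1 Day 1 and Day 15 at pre-dose and 1, 2, 4, 5, 6, 8, 12 hours and 24 hours post-dose", plus one pre-dose ECG on Day 8. It also lets the Safety Monitoring Committee waive the Day 15/16 series.

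The SAP text does not say whether the two structures describe the residuals or the random effects, which fit is primary, how the degrees of freedom are obtained, or what happens if a fit does not converge.

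**The concern.** A random subject factor already induces a constant within-subject correlation. Adding residual compound symmetry models the same thing twice, and adding a residual unstructured matrix over a dense ECG schedule asks for a very large number of variance parameters. Neither step addresses the feature that matters most for the reported slope, namely whether subjects differ in their QTcF response to concentration.

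If they do differ, a model with only a random intercept treats all of a subject's readings as separate information on one shared slope, and its standard error is then too small. Protocol 7.4.5.1 plans an exposure-response slope analysis for QTcF, and Protocol 3.3.1 says prolongation is being investigated in Part 1, so an interval that overstates precision could understate the QT effect still compatible with the data. Two structures on two data sets also give 2 x 2 = 4 slope estimates, with no rule for which one is the result.

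**Working it through.** **Plan figures reproduced.** Protocol 8.1.1 anticipates 36 subjects: 5x3 + 2x6 + 1x9 = 36, capped at 42. The Cycle 1 PK volume is (10 + 1 + 10) samples x 3 mL = 63 mL, as stated, and every ECG time has a matching PK time.

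**Post-baseline times.** Day 1 has 9, Day 8 has 1 and Day 15/16 has 9, so 19 in total. Less the baseline, T = 18.

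**Residual unstructured matrix, T(T+1)/2 parameters.**
- Cycle 1: 18x19/2 = 171. With 36 subjects there are 36x18 = 648 values, 3.8 per parameter; with 42 there are 756, or 4.4.
- Day 15/16 waived: 8 + 1 = 9 times, 9x10/2 = 45.
- Data to cut-off with, say, three later visits: 21x22/2 = 231.

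**Redundancy.** Write J for the all-ones matrix and I for the identity.
- Random intercept plus residual compound symmetry is aJ + bJ + cI. This has three parameters but rank 2, because only a + b is identified. It is a plain random-intercept model.
- Random intercept plus residual unstructured has 172 parameters and rank 171, because J already lies inside the unstructured matrix.
- If the structures apply to the random effect as worded, subject alone gives a 1x1 matrix, and the two fits coincide.

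**Simulation.** 36 subjects on the protocol's dose scenario, 18 times, complete data, true slope 0, REML, intervals at +/-1.96 SE. Assumed, not in the documents: intercept SD 6 ms, residual SD 7 ms, one-compartment kinetics with a 12 h half-life, and the between-subject slope SD, expressed in ms at top-dose Cmax. Each cell gives coverage of the nominal 95% interval, then model SE divided by the true SD of the estimate.

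| Slope SD (ms) | Random intercept / CS | Random intercept + slope | Residual unstructured |
|---|---|---|---|
| 0 | 93%, 0.98 | 94%, 1.00 | 62%, 0.46 |
| 1 | 93%, 0.94 | 91%, 0.98 | 69%, 0.47 |
| 2 | 91%, 0.88 | 96%, 1.01 | 69%, 0.54 |
| 5 | 83%, 0.71 | 93%, 0.94 | 58%, 0.41 |
| 10 | 66%, 0.48 | 92%, 0.92 | 52%, 0.38 |

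The random-intercept rows at 0, 2 and 5 ms use 400 runs; all other cells use 150. Monte Carlo standard error at 150 runs is sqrt(0.95x0.05/150) = 1.8 points near 95% and sqrt(0.6x0.4/150) = 4 points near 60%. At 400 runs it is 1.1 points near 95% and sqrt(0.83x0.17/400) = 1.9 points near 83%. With a t quantile on 33 df, random-intercept coverage is 95%, 92% and 85% at 0, 2 and 5 ms.

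The table shows two separate effects. The unstructured fit undercovers even with no slope variation, so its cause is unstable covariance estimation. The random-intercept fit undercovers only as slope variation grows.

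**The case against.** The strongest reply is that the code sits in shells that are not among the documents. The two structures could describe the between-subject matrix of a random intercept and slope, which would remove both the redundancy and the omission. That possibility stands. The SAP text does not say it, however, and under that reading compound symmetry would force equal variances on an intercept and a slope measured in different units, so a primary fit would still have to be named. The wording could also be loose for a residual structure with subject as the clustering unit. Compound symmetry is then an ordinary, identifiable model, but the unstructured fit keeps its 171 parameters.

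A reader might infer that the reported interval is too narrow as a matter of fact. The documents do not support that. They give no between-subject slope variance, and at zero the random-intercept interval is sound. The unstructured result is also conditional: a small-sample correction, which the SAP neither names nor excludes, would change it.

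A reader might also infer that the unstructured fit is impossible, pointing to the 17 subjects treated by March 2019 (Protocol 3.3.1). That is an interim count, not the analysis sample. With 36 to 42 complete subjects there are more subjects than times, so the fit is impractical rather than impossible, and a Day 15/16 waiver would cut it to 45 parameters.

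Finally, the slope is not the only QT output. SAP 15.7 also gives summaries by time point, counts of potentially significant values and a shift table. All analyses are descriptive (SAP 9, Protocol 8.5.1), and no stated decision rests on the slope interval.

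**Conclusion.** The point holds in a conditional form. As the SAP text stands, the covariance pair yields at most one usable fit, a random-intercept model with a common concentration slope. Following the text on the residual reading also produces an unstructured fit whose uncorrected nominal 95% interval covered 52-69% with 36 complete subjects, whatever the slope variation.

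The random-intercept interval may be too narrow. The loss is nil at slope SD 0, small at 1-2 ms and material from about 5 ms at top-dose Cmax (83%, then 66% at 10 ms). These figures depend on the assumed SDs and kinetics; the parameter counts and rank results do not. If the shells already contain a by-subject slope, what remains is to align the SAP text with them. Because the analysis is descriptive, this is a worthwhile correction of modest consequence.

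**What to change.** In SAP 15.7, specify one primary model on the Cycle 1 data:
- Fixed effects: baseline QTcF and concentration. A nominal-time term is optional.
- Random effects: intercept and concentration slope by subject, with a 2x2 unstructured between-subject matrix (4 variance parameters including the residual).
- Independent residuals and a named small-sample degrees-of-freedom method, such as Kenward-Roger.
- Fallback to a random intercept only if the model does not converge or the slope variance is estimated at zero, with the fallback reported.

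Drop the residual unstructured fit. Keep compound symmetry or random intercept only as a labelled sensitivity analysis, and label the run on all data to cut-off as secondary. Check the shells and make text and code agree.

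The cost is SAP wording and code, plus a somewhat wider interval. In the simulation the mean SE rose from 0.643 to 0.675 with no slope variation (0.675/0.643 = 1.05), and from 0.650 to 0.836 at 5 ms (1.29), where the extra width is needed.
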